5.2 Secondary Outcomes

- 5.2.1 Adverse events/toxicity at weeks 4, 8 and every 4 weeks thereafter if remain on treatment
- 5.2.2 Identification of measured phenolic levels (total and component phenolics) at baseline,4, and 8 weeks
- 5.2.3 Evaluate change in systemic cytokines, growth factors from baseline to 4 and 8 weeks including but not limited to: TNF α , IL6, IL6R, IL8, IL1 α , IL1 β , IGF-1, VEGF
- 5.2.4 Overall response rate (CR, PR, and SD) at 8 weeks.
- 5.2.5 PFS and OS in patients with metastatic cancer receiving MGE under the proposed regimen.
- 5.2.6 Quality of life in cancer patients taking MGE using the Functional Assessment of Cancer Therapy–General (FACT-G) measure and fatigue, as measured by the PROMIS Fatigue-Short Form.
- 5.2.7 Adherence to MGE treatment, as assessed by patient-reported medication logs and pill count every 4 weeks while on treatment.

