6.5 Duration of Therapy

In the absence of treatment delays due to adverse events, treatment may continue until one of the following criteria applies:

- Disease progression, either by standard imaging or clinical parameters per the judgment of the treating physician,
- Intercurrent illness that prevents further administration of treatment,
- Unacceptable adverse event(s),
- Patient decides to withdraw from the study, or
- General or specific changes in the patient's condition render the patient unacceptable for further treatment in the judgment of the treating physician.

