6.6 Duration of Follow Up

Patients removed from the study for unacceptable adverse events will be followed until resolution or stabilization of the adverse event. Patients who are removed or withdraw from the study for any reason other than toxicity will be followed for vital status only after the 24 hour washout period. Patients will be followed every 6 ± 2 weeks until death for monitoring survival study endpoints.

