7.0 Measurement of Effect

Although response is not the primary endpoint of this trial, patients with measurable disease will be assessed by the treating physician, based on the clinical radiologic report and clinical status, per usual care. For the purposes of this study, patients will be reevaluated with imaging 8 weeks (± 7 days) after study initiation and then every 12 weeks (± 28 days) while on MGE.

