7.1 Definitions

Evaluable for toxicity (primary outcome): All patients will be evaluable for toxicity from the time of their first treatment with MGE. Per section 6.5.1, patients who miss 7 consecutive days of treatment in the first 28 days for reasons other than toxicity are not evaluable and will be removed from the study and replaced.

Inevaluable for objective response: When no imaging/measurement is done at all at a particular time point, the patient is not evaluable (NE) at that time point.

Measurable disease: Measurable lesions are defined as those that can be accurately measured in at least one dimension (longest diameter in the plane of measurement is to be recorded) with a minimum size of 10 mm by CT scan, 10 mm caliper measurement by clinical exam, or 20 mm by chest X-ray.

Non-measurable lesions: Non-measurable lesions include: bony metastases, leptomeningeal disease, ascites, pleural or pericardial effusion, inflammatory breast disease, lymphangitic involvement of skin or lung, abdominal masses or organomegaly identified by physical exam that is not measurable by reproducible imaging techniques.

Progression-Free Survival is defined as the duration of time from the start of treatment to the time of progression or death. Patients will be followed until disease progression and death.

Overall Survival is defined as the duration of time from the start of treatment to date of death.

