12.2 Analysis of Secondary Objective

12.2.1 To monitor toxicity at 4, 8, and every 4 weeks thereafter on MGE

To analyze objective 2.1.1, we will summarize any expected toxicities, any laboratory based toxicities, and any grade 3 or higher gastrointestinal toxicities and any grade 4 or higher toxicities using frequency tables overall and by week.

12.2.2 To evaluate change in phenolic levels (total and component, blood and urine) from baseline to 4 and 8 weeks

To analyze objective 2.2.2, we will fit a mixed model ANOVA model with phenolic level as the outcome and time (baseline, 4, and 8 weeks) as a fixed effect and subject as a random effect. We will use contrasts to estimate the changes from baseline to week 4 and week 8.

12.2.3 To evaluate change in serum cytokines and growth factors from baseline to 4 and 8 weeks on MGE

To analyze objective 2.2.3, we will fit a mixed model ANOVA model with the outcome of interest (cytokine or growth factor) as the outcome and time (baseline, 4, and 8 weeks) as a fixed effect and subject as a random effect.

We will use contrasts to estimate the changes from baseline to week 4 and week 8.

12.2.4 To observe the response rate of MGE in patients with metastatic cancer.

To analyze objective 2.2.4, we will characterize response at 8 weeks using frequency table. We will also characterize the best response at the end of treatment with MGE using a frequency table.

12.2.5 To assess overall and progression-free survival in patients with metastatic cancer receiving MGE.

To analyze objective 2.2.5, we will summarize overall survival and progression-free survival using the Kaplan-Meier method. We will calculate median survival rates and associated 95% confidence intervals. Patients will be censored at date of last contact.

12.2.6 To assess global quality of life and fatigue in cancer patients taking MGE.

Quality of Life and fatigue will be monitored every 4 weeks until the end of the study. To analyze objective 2.2.6, we will fit a mixed model ANOVA model with phenolic level as the outcome and time (baseline, every 4 weeks) as a fixed effect and subject as a random effect. We will use contrasts to estimate the changes from baseline to each follow-up time period.

12.2.7 To assess adherence to MGE treatment.

To analyze objective 2.2.7, we will summarize the percent of pills taken at the end of every 4 week period i using the formula:

Percent of pills taken_i =

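### Section 7.1 lets patients who die or stop for clinical progression before the 8-week scan be coded not evaluable, and no denominator is set, so the 8-week response rate could be inflated if such patients are left out

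*Combined protocol and SAP*

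**What the plan says.** The rule for a missing assessment is in Section 7.1: "When no imaging/measurement is done at all at a particular time point, the patient is not evaluable (NE) at that time point". It carries no exception for death or for progression already established by other means.

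The endpoint in Section 5.2.4 is "Overall response rate (CR, PR, and SD) at 8 weeks", so stable disease counts as response. For the analysis, Section 12.2.4 says "we will characterize response at 8 weeks using frequency table", and adds "We will also characterize the best response at the end of treatment with MGE using a frequency table". Neither section names an analysis set or a denominator, or says how NE patients are counted.

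Four other places determine who has an assessment at Week 8:

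- Section 7.0: "patients will be reevaluated with imaging 8 weeks (± 7 days) after study initiation". This is the first scan on study.
- Section 6.5 lists as a reason to end treatment: "Disease progression, either by standard imaging or clinical parameters per the judgment of the treating physician". Progression without a scan is accepted.
- Section 6.6: patients who leave for any reason other than toxicity "will be followed for vital status only after the 24 hour washout period". The off-study column of the Section 6.1 table likewise lists vital status only.
- Section 6.2.2 removes patients with a DLT from the study.

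Progression-free survival in Section 7.1 "is defined as the duration of time from the start of treatment to the time of progression or death".

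**The concern.** A patient who stops MGE in Week 5 for clinical progression has progressed under Section 6.5 and is a PFS event under Section 7.1. Study procedures give that patient no Week 8 scan, so the missing-assessment rule, read literally, makes the response code NE and not PD. A patient who dies before Week 8 is also a PFS event and also NE for response. In both cases the outcome is known, and it is a failure.

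Because stable disease counts as response, what separates success from failure at Week 8 is largely whether the patient has progressed. Early progressors and early deaths are the patients the rate must not lose. If they drop out of the denominator, the rate describes those who did well enough to stay on MGE until the scan.

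The population makes such exits plausible. Section 3.1 admits patients with metastatic or unresectable disease who have failed, declined or are unsuited to standard therapy, with ECOG status up to 2 and a required life expectancy of only 3 months.

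**Working it through.** **The plan's own figures.** No response rate, target or power is stated, so there is none to reproduce. The only sample-size figure is the range of 2 to 30 in Section 12.3. The maximum follows from the design: 5 dose levels × 6 patients = 30. At 2 patients per month, 30/2 = 15 months, which agrees with the stated accrual of under 16 months. The response denominator can therefore be at most 30.

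**Path of a patient with clinical progression in Week 5.**

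1. Section 6.5: treatment ends for disease progression.
2. Section 6.6: after washout, only vital status is followed.
3. Section 7.0: the first on-study scan would have fallen at 8 weeks ± 7 days, so no study scan is obtained.
4. Section 7.1: with no imaging or measurement at Week 8, the code is NE.
5. Sections 5.2.4 and 12.2.4: nothing says whether NE is counted in the denominator.

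A death before Week 8 reaches step 4 directly. A patient removed for a DLT before Week 8 can reach it through Section 6.2.2.

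**Size if NE patients are left out.** Let N be the number treated, x the number with CR, PR or SD at Week 8, and k the number without an assessment.

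- Rate over all treated = x/N
- Rate with NE dropped = x/(N − k)
- Ratio of the two = N/(N − k) = 1/(1 − k/N)

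All counts below are assumptions; the documents give none.

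| N | x | k | x/N | x/(N − k) | Ratio |
|---|---|---|---|---|---|
| 18 | 5 | 4 | 27.8% | 5/14 = 35.7% | 1.29 |
| 18 | 5 | 6 | 27.8% | 5/12 = 41.7% | 1.50 |
| 18 | 5 | 8 | 27.8% | 5/10 = 50.0% | 1.80 |
| 30 | 9 | 3 | 30.0% | 9/27 = 33.3% | 1.11 |
| 30 | 9 | 6 | 30.0% | 9/24 = 37.5% | 1.25 |
| 30 | 9 | 9 | 30.0% | 9/21 = 42.9% | 1.43 |
| 30 | 9 | 12 | 30.0% | 9/18 = 50.0% | 1.67 |

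Exact 95% intervals are wide: 14.7% to 49.4% for 9/30 and 26.0% to 74.0% for 9/18. The shift is small against sampling error, but it always goes the same way.

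**How large k might be.** Suppose time to failure is exponential with median m months. The share failing by day 56 is 1 − 0.5^((56/30.4375)/m): 47% for m = 2, 35% for m = 3 and 27% for m = 4. These medians are assumptions, and some of these failures would be found only at the Week 8 scan itself. The shares therefore indicate scale and do not estimate k.

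**The case against.** **A reader might infer that the plan excludes NE patients from the rate.** It does not say so. Section 7.1 labels a patient at one time point and removes nobody from an analysis set. A frequency table can carry an NE row over all treated patients. This objection stands: the inflation is conditional. What remains is that nothing requires the all-treated reading.

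**Clinical progression may be recordable as PD.** Section 7.0 bases assessment on clinical status as well as the radiology report. The data collection table lists a monthly treatment response form and an off-study best-response form. Caliper measurements and usual-care imaging also count under Sections 7.1 and 7.2, so a patient who stops clinically is not automatically NE. Appendices D and E might settle the coding, but they are separate attachments and were not available. This stands in part: the NE rule does not refer to any of this, and no visible text covers death.

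**A reader might infer a contradiction with PFS, or that death is treated as progression.** Section 7.1 makes death a PFS event, not progression, and a patient can be an event for PFS while lacking an objective response assessment. Patients leaving for toxicity are nowhere treated as progressed. The problem is a coding rule that discards a known outcome; the two definitions can coexist.

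**A reader might infer that an inflated rate would drive dose escalation.** Through the five levels, Section 6.2.1 escalates on DLTs alone. Section 12.1 mentions anti-tumor efficacy only for the discretionary decision if no MTD is found after level 5, and it does not name the 8-week rate.

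**The illustrations are not forecasts.** That is correct. Losing 8 of 18 patients (44%) before the scan is a high case, given the 3-month life expectancy criterion and the minimal adverse events expected in Section 8.1.

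**Conclusion.** The point holds in a limited form. As written, the NE rule can absorb patients whose failure before Week 8 is already known, and the plan sets no denominator for either the 8-week or the best-response table. If NE patients are left out, the CR + PR + SD rate is multiplied by 1/(1 − k/N). For assumed early-loss shares of 10% to 40%, that factor is 1.11 to 1.67. In the 18-patient illustration, 28% becomes 36% to 50%.

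This rests on three assumptions: that some patients leave or die before the scan, that they are coded NE and not PD, and that NE patients are omitted from the denominator. The text permits each and establishes none.

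The primary objective is unaffected. Response is a descriptive secondary endpoint with no test or threshold, so the consequence is for interpretation, and at most for the discretionary decision after dose level 5. It is still worth settling before data are seen, because a denominator chosen afterwards can be chosen for the result it gives.

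**What to change.** **Section 7.1.** Limit NE to a missing assessment in a patient who is alive and has not progressed by imaging or clinical parameters. Code clinical progression before the Week 8 scan as PD. Count death from any cause before the scan as non-response. Any cause is the workable rule, because the visible follow-up collects vital status and not cause of death.

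**Section 12.2.4, for both the 8-week and best-response tables.**

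- Take as denominator all patients who received MGE and were planned for response assessment at baseline. Section 7.0 ties assessment to measurable disease, which Section 3.1 does not require. Report patients without measurable disease separately, so that they are not counted as failures of an assessment never planned for them.
- Count patients without a Week 8 assessment as non-responders.
- Show the remaining NE patients as a row, with the reason.

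**Forms.** Confirm that the Off Study form records the reason for leaving; its content is not visible in the documents. Check that Appendices D and E use the same coding.

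**Cost.** Protocol and SAP wording, plus a form change if the reason for leaving is not already recorded. No visits, scans or patients are added. The downside is a slightly less favourable reported rate.

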7.2 Methods for Evaluation of Measurable Disease

The same method of assessment and the same technique should be used to characterize each identified and reported lesion at baseline and during follow-up whenever possible. Measurements will be obtained from usual care imaging and assessed by the PI(s) in confirmation with the physician of record.

- CT is the best currently available and reproducible method to measure lesions selected for response assessment. MRI and PET/CT are also acceptable.
- Lesions on a chest X-ray may be considered measurable lesions if they are clearly defined and surrounded by aerated lung. However, CT is preferable.
- Clinical lesions will only be considered measurable when they are superficial and ≥10 mm in diameter as assessed using calipers. For the case of skin lesions, documentation by color photography, including a ruler to estimate the size of the lesion, is recommended.
- Tumor markers alone will not typically be used to define response. If markers are initially above the upper normal limit, they must normalize for a patient to be considered in complete response.
- Cytology and histology can be used in rare cases (e.g., for evaluation of residual masses to differentiate between Partial Response and Complete Response or evaluation of new or enlarging effusions to differentiate between Progressive Disease and Response/Stable Disease).

8.0 Adverse Events List and Reporting Requirements

8.1 Adverse Event List for MGE

Expected: Based on previous studies, only minimal AEs are expected, including flatulence, diarrhea, nausea, dyspepsia, and abdominal cramping.

8.2 Adverse Event Characteristics

- CTCAE term (AE description) and grade: The descriptions and grading scales found in the revised NCI Common Terminology Criteria for Adverse Events (CTCAE) version 4.0 will be utilized for AE reporting. All appropriate treatment areas should have access to a copy of the CTCAE version 4.0. A copy of the CTCAE version 4.0 can be downloaded from the CTEP web site (http://ctep.cancer.gov).
- **'Expectedness'**: AEs can be 'Unexpected' or 'Expected' (see Section 8.1 above) for expedited reporting purposes only.
- Attribution of the AE:
 - Definite: The AE is clearly related to the study treatment.
 - Probable: The AE **is likely related** to the study treatment.
 - Possible: The AE **may be related** to the study treatment.
 - Unlikely: The AE **is doubtfully related** to the study treatment.
 - Unrelated: The AE **is clearly NOT related** to the study treatment.

8.3 STRC SAE Reporting Requirements

The Safety and Toxicity Reporting Committee (STRC) is responsible for reviewing SAEs for CCCWFU Institutional studies as outlined in Appendix C. STRC currently requires that all unexpected 4 and all grade 5 SAEs on these trials be reported to them for review. All CCCWFU Clinical Research Management (CRM) staff members assisting a Principal Investigator in investigating, documenting and reporting an SAE qualifying for STRC reporting are responsible for informing a clinical member of the STRC as well as the entire committee via the email notification procedure of the occurrence of an SAE.

8.4 WFUHS IRB AE Reporting Requirements

Any unanticipated problems involving risks to subjects or others and adverse events shall be promptly reported to the IRB, according to institutional policy. Reporting to the IRB is required regardless of the funding source, study sponsor, or whether the event involves an investigational or marketed drug, biologic or device. Reportable events are not limited to physical injury, but include psychological, economic and social harm. Reportable events may arise as a result of drugs, biological agents, devices, procedures or other interventions, or as a result of questionnaires, surveys, observations or other interactions with research subjects.

All members of the research team are responsible for the appropriate reporting to the IRB and other applicable parties of unanticipated problems involving risk to subjects or others. The Principal Investigator, however, is ultimately responsible for ensuring the prompt reporting of unanticipated problems involving risk to subjects or others to the IRB. The

Principal Investigator is also responsible for ensuring that all reported unanticipated risks to subjects and others which they receive are reviewed to determine whether the report represents a change in the risks and/or benefits to study participants, and whether any changes in the informed consent, protocol or other study-related documents are required.

Any unanticipated problems involving risks to subjects or others occurring at a site where the study has been approved by the WFUHS IRB (internal events) must be reported to the WFUHS IRB within 7 calendar days of the investigator or other members of the study team becoming aware of the event.

Any event, incident, experience, or outcome that alters the risk versus potential benefit of the research and as a result warrants a substantive change in the research protocol or informed consent process/document in order to insure the safety, rights or welfare of research subjects.

9.0 Pharmaceutical Information

Muscadine grape extract is a nutraceutical compound.

A list of the adverse events and potential risks associated with the investigational agent administered in this study can be found in Section 8.0.

9.1 Drug Accountability

Drug accountability logs will be provided and maintained by the Wake Forest Investigational Drug Services for the investigative agent (MGE) used under this protocol. These logs shall record quantities of study drug received and quantities dispensed to patients, including lot number, date dispensed, patient identifier number, protocol number, dose, quantity returned, balance remaining, and the initials of the person dispensing the medication.

9.2 Muscadine Grape Extract (MGE)

Product description: MGE will be supplied by Nature's Pearl (Advance, North Carolina). The muscadine grapes are pressed and processed on site per good manufacturing practice (FDA Code of Federal Regulations 21). The extract is dried and converted to powder at Pharmachem Laboratories, Inc (Kearny, New Jersey). The MGE is encapsulated with a vegetable capsule of hypromellose obtained from CapsCanada (Pompano Beach, Florida), bottled, and labeled at Nature's Pearl. Quality control testing for antimicrobial contamination (aerobic count, yeast and mold, E.coli/coliform, staph aureus, enterobacteriaceae, and salmonella) and phenolic levels occurs numerous times during the production process.

Storage requirements: Capsules should be stored at room temperature.

Route of administration: MGE is available for oral administration.

10.0 Laboratory Studies

10.1 Phenolic assays

Total and component phenolics will be measured from blood and urine at baseline, 4 weeks, and 8 weeks if the patient remains on MGE. Blood assays will require approximately 10ml of blood. For the polyphenolic analysis²⁶ one tube of blood at each time point will be collected in tubes containing EDTA and ascorbic acid and stored at - 80°C for an indefinite period of time. The blood sample will be thawed on ice and used to measure polyphenols by ultra-high performance liquid chromatography (UPLC) coupled to mass spectroscopy detection (UPLC-MS).

A spot urine collection will be collected at baseline, 4 weeks, and 8 weeks if the patient remains on treatment with MGE. The urine will be collected into a urine collection cup and mixed with ascorbic acid; 20 mL aliquots will be stored at -80°C for an indefinite period of time. The urine will be thawed on ice and used to measure polyphenols by UPLC-MS.

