2.2 Secondary Objectives

- 2.2.1 To monitor adverse events/toxicity every 4 weeks while on treatment
- 2.2.2 To evaluate change in phenolic levels (total and component, blood and urine) from baseline to 4 and 8 weeks on MGE
- 2.2.3 To evaluate change in serum cytokines and growth factors from baseline to 4 and 8 weeks on MGE
- 2.2.4 To observe the response rate of MGE in patients with metastatic cancer.
- 2.2.5 To assess overall and progression-free survival in patients with metastatic cancer receiving MGE.
- 2.2.6 To assess global quality of life (FACT-G) and fatigue (PROMIS-fatigue short form) in cancer patients taking MGE.
- 2.2.7 To assess adherence to MGE treatment.

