3.0 Patient Selection

3.1 Inclusion Criteria

3.1.1 Patients must have histologically confirmed solid tumor malignancy (excluding primary brain tumor) that is metastatic or unresectable and have failed standard therapies. Patients are also eligible if patients declined (or if their physicians determined them unsuitable for) standard therapy options.

$3.1.2 \ge 18$ years of age

- 3.1.3 The effects of MGE on the developing human fetus are unknown. Women of child-bearing potential and men must agree to use adequate contraception (hormonal or barrier method of birth control; abstinence) prior to study entry and for the duration of study participation. Should a woman become pregnant or suspect she is pregnant while participating in this study, she should inform her treating physician immediately.
- 3.1.4 Ability to understand and the willingness to sign an IRB-approved informed consent document.
- 3.1.5 ECOG performance status ≤ 2 .
- 3.1.6 Patients must have adequate organ and marrow function as defined below:
 - absolute neutrophil count >1000/mcL
 - platelets >50,000/mcL
 - total bilirubin
- within normal institutional limits
- AST(SGOT)/ALT(SGPT) <2.5 X institutional upper limit of normal
- creatinine clearance >40 mL/min
- 3.1.7 Stable supplement usage for >2 weeks prior to starting and agrees not to change while on this study.
- 3.1.8 Life expectancy \geq 3 months
- 3.1.9 Patients who declined standard therapies or whose physicians determined they were not suitable for standard therapy options are eligible.

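### Urine phenolics come from an untimed spot sample with no stated dilution correction, so the planned change from baseline carries visit-to-visit urine dilution

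*Combined protocol and SAP*

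**What the plan says.** Section 2.2.2 sets the objective: "To evaluate change in phenolic levels (total and component, blood and urine) from baseline to 4 and 8 weeks on MGE". Section 5.2.2 gives the outcome as "Identification of measured phenolic levels (total and component phenolics) at baseline,4, and 8 weeks", with no units and no normalised quantity.

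On collection, section 10.1 says: "A spot urine collection will be collected at baseline, 4 weeks, and 8 weeks if the patient remains on treatment with MGE". On handling: "The urine will be collected into a urine collection cup and mixed with ascorbic acid; 20 mL aliquots will be stored at -80°C". On the assay: "The urine will be thawed on ice and used to measure polyphenols by UPLC-MS". It sets no collection interval, total volume, time of day or time since the last capsule.

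On analysis, section 12.2.2 says that "we will fit a mixed model ANOVA model with phenolic level as the outcome and time (baseline, 4, and 8 weeks) as a fixed effect", with subject as a random effect and contrasts for the changes to Weeks 4 and 8. It mentions no dilution covariate, normalisation or transformation.

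As an on-study measurement, creatinine appears only in the serum panel (section 6.1, footnote d, repeated in Appendices I and J). Neither the schedule in 6.1 nor section 10.1 provides for urine creatinine, specific gravity or osmolality.

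**The concern.** A phenolic concentration in spot urine depends on how much phenolic is being excreted and on how much water it is excreted in. Without a volume and an interval, an excreted amount cannot be derived. Without a dilution marker, the two components cannot be separated. Fluid intake, diuretics, intravenous fluids and intercurrent illness can all move the concentration while excretion stays constant. Timing after the dose is a separate matter: two samples taken at the same hour after a capsule can still differ in dilution.

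At stake is the urine half of one secondary objective. With at most three samples per patient and 2 to 30 patients, extra within-patient noise makes a real change harder to see. Any drift in hydration that coincides with treatment would be read as a change in phenolic exposure.

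**Working it through.** The plan gives no figure for urine variability, so there is none to reproduce. The check has two parts: what the model removes, and how much may be left.

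**1. What the subject effect removes.** On the log scale, write patient *i*'s urine level at visit *j* as

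y_ij = μ_j + b_i + e_ij + d_ij,

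where b_i is the patient's stable level, including usual dilution, e_ij is visit-to-visit variation in excretion (SD s_e), and d_ij is visit-to-visit variation in dilution (SD s_d). The change from baseline is

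y_ij − y_i0 = (μ_j − μ_0) + (e_ij − e_i0) + (d_ij − d_i0).

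The stable term b_i cancels and the dilution term does not. With independent errors, the variance of the change is 2(s_e² + s_d²) without correction and 2s_e² with an ideal correction.

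**2. Size for one patient, dilution alone.** Assume s_d = 0.3, 0.5 or 0.7. The 95% range of the change ratio is exp(1.96 × √2 × s_d) either way:

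| s_d (assumed) | 1.96 × √2 × s_d | Fold, either way |
|---|---|---|
| 0.3 | 0.83 | 2.3 |
| 0.5 | 1.39 | 4.0 |
| 0.7 | 1.94 | 7.0 |

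**3. Size for the mean.** Take 15 patients, that is 5 dose levels × 3 with no expansion (an assumption; fewer may reach Week 8). With t = 2.145 on 14 df, dilution alone gives a 95% confidence interval for the mean ratio of exp(2.145 × √2 × s_d / √15) = 1.26-, 1.48- or 1.73-fold either way.

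**4. What an ideal correction would gain.** Dilution's share of the variance of the change is s_d² / (s_e² + s_d²). With s_e assumed to be 0.4 to 0.7:
- smallest: 0.09 / (0.49 + 0.09) = 16%
- largest: 0.49 / (0.16 + 0.49) = 75%

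For 20 evaluable patients, s_e = 0.4 and s_d = 0.5:
- uncorrected: exp(1.96 × √(2 × 0.41 / 20)) = 1.49-fold
- corrected: exp(1.96 × √(2 × 0.16 / 20)) = 1.28-fold

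**5. When it becomes bias.** At constant excretion, concentration varies as 1 / urine flow. If mean flow fell to 0.8 of baseline, the apparent level would be 1 / 0.8 = 1.25 times baseline; if it rose to 1.25, the apparent level would be 0.80 times. Without a systematic shift in flow, d_ij − d_i0 averages to zero and only precision is lost.

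**6. Samples affected.** At most 30 patients (section 12.3) × 3 visits = 90.

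**The case against.** The strongest reply is that the text is silent rather than wrong. Section 12.2.2 refers to a level and does not call it raw or a concentration. Section 10.1 is a short assay summary without reporting units, and the Appendix K laboratory form is a separate attachment. A urine creatinine field there cannot be excluded. This stands, and it limits the claim to what the visible text specifies. But neither 10.1 nor 12.2.2 calls for a correction, so an analyst following them would not apply one.

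Second, consequences are limited. Blood phenolics are taken at the same three visits and do not depend on urine dilution. Escalation does not use urine, and 12.2.2 estimates changes without a success threshold. This also stands.

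Third, the SDs are assumed, the calculation is on a log scale that the plan does not state, and no expected rise is given for comparison. By the protocol's own figures, the dose levels supply about 2 × 162 = 324 to 10 × 162 = 1,620 mg phenolics a day, so the rise may be large enough to show through the noise. The figures therefore show how large the dilution component could be. They do not show that a conclusion would be lost.

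A reader might go further and infer that patients will drink less as disease progresses, so that a false rise at Weeks 4 and 8 is to be expected. The documents do not support that. They contain no hydration data. Section 8.1 expects diarrhea and nausea, which could concentrate the urine, but section 6.4 allows full supportive care, which could act either way. Progression is a reason to stop treatment under 6.5, and later samples are taken only from patients still on MGE.

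**Conclusion.** The point holds as a limited one. On the visible text, the urine part of objective 2.2.2 is analysed without a dilution correction, and visit-to-visit dilution stays in the baseline contrasts. The expected harm is lost precision: about 2.3- to 7.0-fold either way for one patient's ratio, if the within-patient log SD of dilution is 0.3 to 0.7. That range is an assumption. Bias in the mean change needs a systematic hydration shift, which the documents do not show but which the design, without a control arm, could not detect. It would be too strong to call the urine result uninterpretable or the phenolic objective lost, because the blood measure is untouched. The primary outcome, MTD and sample size are not affected. This is a cheap improvement worth making, not a flaw in the trial's main question.

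**What to change.** In section 10.1, add a creatinine measurement on the stored urine aliquots, by a method that the laboratory confirms is not affected by the added ascorbic acid. In 10.1 and 12.2.2, define the urine outcome as phenolic corrected for urine creatinine, and keep the uncorrected concentration as a sensitivity analysis. If Appendix K already records urine creatinine, only the outcome definition and the analysis sentence need to change.

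If specific gravity is wanted as a check, read it on fresh urine before ascorbic acid goes in. A reading on the preserved aliquot would include the added solute.

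The cost is one extra assay on at most about 90 samples and a few lines of text. Creatinine needs no new visit, sample or patient procedure; the optional specific gravity reading adds a step at collection. One drawback is that creatinine excretion may fall with muscle loss in this population, which would inflate the corrected ratio over time. Reporting the uncorrected result alongside lets a reader see whether the conclusion depends on the correction. Fixing the choice in advance also prevents selection between the two after the data are seen.
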